6.1 Evaluation of QT/RR Correction Methods

In case a substantial HR effect is observed, defined as the largest LS mean $\Delta\Delta\text{HR}$ greater than 10 bpm, the relationship between QTc (QTcF and, if derived, QTcS [individual], QTcI [optimized] using unadjusted RR, 1-minute average RR, 3-minutes average RR, 1-minute weighted average RR and 3-minutes weighted average RR) and RR interval will be investigated using on-treatment data (LOXO-305, and moxifloxacin) by a linear regression model: $QTc = c + d \times RR$. Mean QTc and RR values from all nominal time points (including pre-dose) will be used. The RR coefficient for each subject, d_i , will then be used to calculate the average sum of squared slopes (SSS) for each of the different QT/RR correction methods. In addition, a scatter plot and quantile plot of QTc (QTcF, QTcS, QTcI) and RR intervals by treatment with a regression line and a linear mixed-effects line (90% CI), respectively, will also be given. QTcI based on a 3-minute weighted average will be used as the primary endpoint, with other corrections as supporting evidence.

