8.3.3. Evaluation for QT-RR Correction Methods

In case a substantial HR effect is observed, defined as a largest $\Delta\Delta HR$ greater than 10 bpm, the relationship between QTc (QTcF and, if derived, QTcS [individual], and QTcI [optimized]) and RR interval will be investigated using on-treatment data (LOXO-305, moxifloxacin, and placebo) by a linear regression model: $QTc = c + d \times RR$. Mean QTc and RR values from all nominal time points (including predose) will be used. The RR coefficient for each subject, d_i , will then be used to calculate the average sum of squared slopes (SSS) for each of the different QT/RR correction methods. The correction method that results in the average on-treatment slope closest to 0 (the smallest average SSS, as described by Tornøe et al 2011¹⁷) for LOXO-305 and placebo will be deemed the most appropriate HR correction method. If different methods show similar SSS values on placebo as on LOXO-305, priority in the choice will be given to the placebo results. In addition, a scatter plot and quantile plot of QTc (QTcF, QTcS, and QTcI) and RR intervals by treatment with regression line and a linear mixed-effects line (90% CI), respectively, will also be given.

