For QTcS and QTcI, the individual correction coefficients, b_i , will be listed and also summarized in a table using arithmetic mean, SE, number of subjects, and 90% CI (based on a *t*-distribution).

The method that removes the HR dependence of the QT interval most efficiently will be chosen as the primary correction method.

6 Analyses

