8.1 Tables

Number	Title	Comments
14.1.1	QTcS and QTcI individual correction coefficients with descriptive statistics	Number of subjects (n), mean, SD, SE, 90% CI, median, minimum, and maximum will be given (Section 5.4).
14.1.2	Average SSS for different QT-RR correction methods	SSS for LOXO-305, moxifloxacin, and placebo will be given (Section 6.1).
14.1.3	Baseline values of ECG parameters with descriptive statistics	Number of subjects (n), mean, SD, SE, 90% CI, median, minimum, and maximum from descriptive analysis will be given by treatment for each ECG parameter (Section 6.4).
14.1.4	Observed values of QTc (primary correction method) with descriptive statistics	n, mean, SD, SE, 90% CI, median, minimum, and maximum from descriptive statistics will be given by treatment and post-dose time point (Section 6.4).

Number	Title	Comments
14.1.5.1- 14.1.5.10	Change-from-baseline QTcF (and QTcI in 5 ways and QTcS if calculated), HR, PR, and QRS (Δ QTcF, Δ QTcI, Δ QTcS, Δ HR, Δ PR, and Δ QRS) at each time point	n, LS mean, SE, and 90% CI from the statistical modeling will be given by treatment and time point (Section 6.4).
14.1.6.1- 14.1.6.10	Placebo-corrected change-from-baseline QTcF (and QTcI in 5 ways and QTcS if calculated), HR, PR, and QRS ($\Delta\Delta$ QTcF, $\Delta\Delta$ QTcI, $\Delta\Delta$ QTcS, $\Delta\Delta$ HR, $\Delta\Delta$ PR, and $\Delta\Delta$ QRS) at each time point	LS mean, SE, and 90% CI from the statistical modeling will be given by treatment and time point (Section 6.4).
14.1.7	QTc outliers per absolute category	Number (%) of subjects and time points with QTc > 450 and ≤ 480 ms, > 480 and ≤ 500 ms, or > 500 ms by treatment (Section 6.5).
14.1.8	QTc outliers per change-from-baseline category	Number (%) of subjects and time points with Δ QTc > 30 and ≤ 60 ms, or > 60 ms by treatment (Section 6.5).
14.1.9	Categorical analyses for HR, PR, and QRS	Number (%) of subjects and time points with Δ PR $> 25\%$ and PR > 200 ms at post-dose; Δ QRS $> 25\%$ and QRS > 120 ms at post-dose; HR decrease from baseline $> 25\%$ and HR < 50 bpm at post-dose; and HR increase from baseline $> 25\%$ and HR > 100 bpm at post-dose (Section 6.5).
14.1.10	T-wave morphology and U-wave presence across treatment groups: treatment-emergent changes	Number (%) of subjects and time points falling into each of the T-wave and U-wave categories will be given by treatment (Section 6.6).

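### SAP 6.1 drops placebo and the protocol's selection rule from the QT-correction evaluation and conflicts with other SAP sections on how the primary correction is set; if the slopes decide, prolongation can be understated

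*SAP*

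**What the plan says.** **When it applies.** Both documents use QTcF unless the largest LS mean placebo-corrected heart-rate change on LOXO-305 exceeds 10 bpm. Above that, QTcS and QTcI may be derived, with coefficients from the placebo period (Protocol 8.3.2, SAP 5.4).

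**Protocol 8.3.3.** The relation between QTc and RR "will be investigated using on-treatment data (LOXO-305, moxifloxacin, and placebo) by a linear regression model". The method with the smallest average SSS "for LOXO-305 and placebo will be deemed the most appropriate HR correction method". A further clause reads: "If different methods show similar SSS values on placebo as on LOXO-305, priority in the choice will be given to the placebo results".

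**SAP 6.1.** The relation "will be investigated using on-treatment data (LOXO-305, and moxifloxacin) by a linear regression model". The section has no smallest-SSS rule and no placebo clause. It ends: "QTcI based on a 3-minute weighted average will be used as the primary endpoint, with other corrections as supporting evidence".

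**Elsewhere in the SAP.** Table 14.1.2, which cites Section 6.1, states: "SSS for LOXO-305, moxifloxacin, and placebo will be given". Section 5.4 states: "The method that removes the HR dependence of the QT interval most efficiently will be chosen as the primary correction method". Section 4.3.1 says the same of the primary endpoint, and 6.2 refers to the correction chosen as primary.

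**The concern.** There are two separate problems.

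The first is consistency. A programmer who follows SAP 6.1 has no placebo slopes to put in Table 14.1.2. A statistician who follows the SAP as a whole finds the primary correction both fixed in advance and chosen from the data.

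The second is bias. The comparison runs only when LOXO-305 has raised heart rate, so RR shortens as concentration rises. A true concentration-driven QTc increase then gives a negative slope of QTc on RR. A correction with too small an exponent leaves a positive slope. The two cancel, so a small SSS on LOXO-305 data can reward the correction that hides the drug effect. The other retained treatment, moxifloxacin, is in the trial because it prolongs QTc. Placebo is the one treatment whose slopes carry no drug effect, and SAP 6.1 leaves it out. The error would run in the unsafe direction for the 10 ms conclusion.

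**Working it through.** **1. The plan's own margin, for scale.** The plan gives no figure for this step. SAP 6.8 assumes a true effect of 3 ms against a 10 ms limit, an SD of 8 ms on each treatment, 24 subjects and 1-sided 5%. The effect size is (10 − 3)/(8 × √2) = 0.619, and the paired t-test power is 90.2%, so the stated 90% reproduces. The planned margin is 7 ms, and any understatement should be read against that.

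**2. The texts side by side.**

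| Item | Protocol 8.3.3 | SAP 6.1 | Elsewhere in SAP |
|---|---|---|---|
| Data for slopes | LOXO-305, moxifloxacin, placebo | LOXO-305, moxifloxacin | Table 14.1.2: all three |
| Selection | smallest average SSS, LOXO-305 and placebo | none stated | 4.3.1 and 5.4: most efficient method |
| Placebo priority | yes, if SSS values are similar | absent | absent |
| Primary correction | chosen | 3-minute weighted QTcI | 4.3.1, 5.4, 6.2: chosen |

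**3. Bias if QTcF is used and the true exponent b is not 1/3.** Assume a true QTc of 400 ms and heart rate rising from 65 to 77 bpm, so RR goes from 60/65 = 0.923 s to 60/77 = 0.779 s. The spurious change in QTcF is 400 × (0.779^(b − 1/3) − 0.923^(b − 1/3)).

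- b = 0.36: 397.3 − 399.1 = −1.8 ms
- b = 0.40: 393.4 − 397.9 = −4.5 ms
- b = 1/3: 0
- b = 0.28: 405.4 − 401.7 = +3.6 ms from unrounded values (overstates, the safe direction)

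**4. Would the SSS pick QTcF?** This was simulated with 400 trials per scenario, 24 subjects, and 3 predose and 13 postdose time points. The candidates were QTcF, QTcS and QTcI, and the smallest mean squared slope won. The following inputs are assumptions, not in the documents: +12 bpm at peak, between-subject exponent SD 0.04, residual SD 4 ms, a moxifloxacin effect of 12 ms, and a nearly unbiased QTcI coefficient. The share of trials selecting QTcF was:

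| True exponent | LOXO-305 effect | LOXO-305 + moxifloxacin (SAP 6.1) | All three | LOXO-305 + placebo | Placebo only |
|---|---|---|---|---|---|
| 0.36 | 0 ms | 50% | 15% | 0% | 0% |
| 0.36 | 5 ms | 85% | 53% | 7% | 0% |
| 0.36 | 10 ms | 94% | 82% | 63% | 0% |
| 0.40 | 0 ms | 33% | 1% | 0% | 0% |
| 0.40 | 5 ms | 98% | 43% | 0% | 0% |
| 0.40 | 10 ms | 100% | 96% | 74% | 0% |

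At exponent 0.28, QTcF was never selected on any data set. When QTcF was selected, it understated the peak effect by about 1.9 ms (0.36) or 4.8 ms (0.40), close to step 3. QTcS and QTcI had almost no bias.

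**5. True exponent of 1/3.** A separate run used approximations of the same candidates, exponent SD 0.02 or 0.04, and drug effects of 0 to 8 ms. Mean hidden prolongation was at most about 0.4 ms.

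**6. SSS as supporting evidence.** At exponent 0.40 with a 10 ms LOXO-305 effect, a nearly unbiased QTcI had a mean SSS of about 0.0020 on LOXO-305, 0.0019 on moxifloxacin and 0.0005 on placebo. A sound correction would look defective on active treatment.

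**The case against.** The strongest objection is the closing sentence of SAP 6.1. If it governs, 3-minute weighted QTcI is primary and no SSS chooses anything. Its coefficients come from the placebo period, so they are already drug-free. This stands for anyone who follows 6.1 alone. It does not settle the matter, because SAP 4.3.1, 5.4 and 6.2 still describe a choice.

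Nothing here runs unless the 10 bpm trigger is met. Protocol 1.4.1 and 3.3.1 report no clinically significant vital-sign or ECG findings in healthy volunteers, including at 900 mg. That makes the branch less likely but does not rule it out; 6 volunteers had received that dose.

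A reader might infer that a correction with an exponent 0.05 or 0.10 too low would be chosen, hiding 3.4 or 6.7 ms. The documents do not support that as a general figure. The candidates are QTcF at 1/3 and two corrections fitted to placebo data, so with a true exponent near 1/3 no such candidate exists.

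A reader might also infer that the SSS is the only evidence, or that the protocol ranks placebo first outright. SAP 6.1 also asks for scatter and quantile plots of QTc against RR by treatment, and the protocol's placebo clause is conditional on similar SSS values. Because Table 14.1.2 still lists placebo, the omission may be a drafting slip.

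Finally, placebo is not a perfect judge. QTcS and QTcI are fitted on the placebo period, so its SSS favours them over QTcF, and its RR range is narrower than on drug.

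**Conclusion.** The point holds as an inconsistency that needs correcting and as a conditional bias. SAP 6.1 departs from Protocol 8.3.3 on the data, the selection rule and the placebo clause. It conflicts with its own Table 14.1.2 and with SAP 4.3.1, 5.4 and 6.2.

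The primary result is affected only if three things hold: the 10 bpm trigger is met, the SSS decides, and the true QT-RR exponent exceeds 1/3. The understatement is then about 2 ms at 0.36 and 4 to 5 ms at 0.40, against a planned margin of 7 ms. At 1/3 or below it is about 0.4 ms or less. These sizes rest on the assumed inputs above and show direction and range only.

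The tempting stronger reading is that the plan as written will mistake a drug effect for rate dependence. The documents do not support it, because SAP 6.1 contains no SSS selection step and names a fixed primary correction. If that sentence governs, the damage is confined to the supporting SSS evidence.

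Returning placebo to the pooled data would not be enough. With a 10 ms effect, all three treatments together still picked QTcF in 82% to 96% of trials at the two higher exponents, and LOXO-305 plus placebo in 63% to 74%.

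**What to change.** In SAP 6.1, restore placebo to the slope data and settle one rule before the heart-rate result is known.

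- **Option (a).** Restore the protocol's SSS selection, with the placebo SSS deciding. Exclude moxifloxacin from the choice and report active-treatment SSS as descriptive. This makes the protocol's conditional placebo priority unconditional, so record the change.
- **Option (b).** Keep 3-minute weighted QTcI as the prespecified primary correction for this branch, state that the SSS is descriptive only, and record the departure from Protocol 8.3.3.

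Align SAP 4.3.1, 5.4, 6.2 and Table 14.1.2 with the option taken. Where placebo SSS is reported, note that it is partly in-sample for QTcS and QTcI.

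The cost is SAP wording and a small programming change, with no new data. The downside is a narrower RR range on placebo, so the comparison may be less precise. Judging the fitted corrections on time points left out of their fit would address the in-sample problem, but it means re-deriving coefficients across five QTcI versions and is an optional extra.

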6.2 Concentration-QTc Analysis (Primary Analysis)

The relationship between LOXO-305 plasma concentrations and change-from-baseline QTc ($\Delta QTcF$, or ΔQTc corrected with the HR correction method chosen as primary if a substantial HR effect is observed) be quantified using a linear mixed-effects modeling approach. The model will include ΔQTc as the dependent variable, LOXO-305 plasma concentrations as the explanatory variate (0 for placebo), centered baseline QTc (i.e., baseline QTc for individual subject minus the population mean baseline QTc for all subjects in the same treatment period) as an additional covariate, treatment (active = 1 or placebo = 0), time (i.e., nominal post-dose time point) as fixed effects, and random effects on the intercept and slope per subject¹. In addition, if there are significant concentrations of LOXO-305 metabolites, their concentrations/QTc relationship may be explored (exploratory metabolite profiling has shown that unchanged LOXO-305 is the major drug-related component in human plasma). In all calculations, zero will be substituted for concentrations below the quantification limit of the assay and for concentrations from subjects who received placebo.

An unstructured covariance matrix will be specified for the random effects. If convergence cannot be achieved even after appropriate rescaling of the concentrations, the random effect on the slope and intercept will be dropped, in this order, until convergence is achieved. The degrees of freedom of estimates will be determined by the Kenward-Roger method. From the model, the slope (i.e., the regression parameter for LOXO-305 concentrations) and the treatment effect-specific intercept (defined as the difference between active and placebo) will be estimated together with the 2-sided 90% CI. The estimates for the time effect will be reported with degrees of freedom and SE.

The geometric mean of the individual C_{max} values for subjects in the active dose group will be determined. The predicted effect and its 2-sided 90% CI for $\Delta\Delta QTc$ (i.e., slope estimate \times concentration + treatment effect-specific intercept) at this geometric mean C_{max} of LOXO-305 will be obtained. If the upper bound of the 2-sided 90% CI of the predicted effect of $\Delta\Delta QTc$ at clinically relevant plasma levels of LOXO-305 is below 10 ms, it will be concluded that LOXO-305 does not cause clinically relevant QTc prolongation within the observed plasma concentration ranges.

To evaluate the adequacy of model fit with respect to the assumption of linearity, the observed ΔQTc values adjusted by population time effect estimated from the model will be used. These individual placebo-adjusted $\Delta QTc_{i,k}$ ($\Delta\Delta QTc_{i,k}$) values equal the observed individual $\Delta QTc_{i,k}$ for subject i administered with active drug or placebo at time point k minus the estimated population mean placebo effect at time point k (i.e., time effect). A quantile plot, i.e. plot of the quantiles (deciles) of observed drug concentrations and the mean placebo-adjusted ΔQTc ($\Delta\Delta QTc$) and 90% CI at the median concentration within each decile will be given. The regression line presenting the model-predicted $\Delta\Delta QTc$ (as described by Tornøe et al²) will be added to evaluate the fit of a linear model and visualize the concentration-response relationship. Additional exploratory analyses (via graphical displays and/or model fitting) will include assessing for a delayed effect (hysteresis, [Section 6.2.1](#)) and the justification for the choice of the pharmacodynamic model (linear versus nonlinear, [Section 6.2.2](#)) as follows.

The SAS code for the concentration-QTc analysis using the full model is as follows.

```
PROC MIXED DATA=PKPD method=reml;
CLASS SUBJID TIME;
MODEL DQTc=TRT CONC TIME CBASE/ solution cl noint alpha=0.1 alphap=0.1 COVB DDFM=KR;
RANDOM INT CONC /type=UN SUBJECT=SUBJID s;
RUN;
```

Where PKPD = PK/QTc population, SUBJID = subject number, TRT = treatment (active = 1 or placebo = 0), TIME = nominal post-dose time point, CONC = time-matched plasma concentration of LOXO-305 (0 for placebo), CBASE = centered baseline QTcF, and DQTc = Δ QTcF.

Note: ESTIMATE statements will be included for the prediction of the effect in the active dose group.

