6.3 Assay Sensitivity

The analysis to show assay sensitivity will be based on the concentration-QTc analysis of the effect on ΔQTc of 400 mg oral moxifloxacin using a similar model as for the primary analysis. That is, the relationship between moxifloxacin plasma concentration and ΔQTc will be investigated by linear mixed-effects modeling. The model will include ΔQTc as the dependent variable, moxifloxacin plasma concentration as the explanatory variable (0 for placebo), centered baseline QTc (i.e., baseline QTc for individual subject minus the population mean baseline QTc for all subjects in the same treatment period) as an additional covariate, study treatment (moxifloxacin = 1 or placebo = 0) and time (i.e., post-dose time point) as fixed effects, and a random intercept and slope per subject (Garnett et al¹). The geometric mean of the individual C_{max} values for subjects receiving the single dose of 400 mg moxifloxacin will be determined. The predicted effect and its 2-sided 90% CI for $\Delta\Delta QTc$ (i.e., slope estimate \times concentration + treatment effect-specific intercept) at this geometric mean C_{max} will be obtained.

If the slope of the moxifloxacin plasma concentration/ ΔQTc relationship is statistically significant at the 10% level in a 2-sided test and the lower bound of the 2-sided 90% CI of the predicted QT effect at the observed geometric C_{max} of the 400 mg dose is above 5 ms, assay sensitivity will be deemed to have been demonstrated.

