6.4 By-Time Point Analysis

The analysis for QTc will be based on a linear mixed-effects model with ΔQTc (ΔQTc_F , or ΔQTc corrected per the HR correction method chosen as primary if a substantial HR effect is observed) as the dependent variable, period, sequence, time (i.e., nominal post-dose time point), treatment (LOXO-305, moxifloxacin and placebo), and time-by-treatment interaction as fixed effects, and baseline QTc as a covariate. An unstructured covariance matrix will be specified for the repeated measures at post-dose time points for subject within treatment period. If the model with unstructured covariance matrix fails to converge, other covariance matrix such as compound symmetry and autoregressive will be considered. The model will also include a subject-specific random effect. If the fixed effects for period and/or sequence should prove to be nonsignificant (that is, if the P value > 0.1), these effects may be removed from the model and the analysis will be repeated without those covariates. From this analysis, the LS mean, SE, and 2-sided 90 % CI will be calculated for the contrast “LOXO-305 versus placebo” at each post-dose time point, separately.

For HR, PR, QRS intervals, and QTc with the methods not selected as primary, the analysis will be based on the change-from-baseline post-dosing values (ΔHR , ΔPR , ΔQRS , and ΔQTc). The same (by-time point analysis) model will be used as described above for QTc. The LS mean, SE, and 2-sided 90% CI from the statistical modeling for both change-from-baseline and placebo-corrected change-from-baseline values will be listed in the tables and graphically displayed.

The SAS code for the by-time point analysis for QTc is as follows.

```
PROC MIXED DATA=ECG;  
CLASS SUBJID TREAT TIME PERIOD SEQUENCE;
```

```
MODEL DQTc=BASE TREAT TIME TREAT*TIME PERIOD SEQUENCE/DDFM=KR;  
RANDOM INTERCEPT / SUBJECT =SUBJID TYPE=UN;  
REPEATED TIME / SUBJECT = PERIOD*SUBJID TYPE = UN;  
LSMEANS TREAT*TIME/CL DIFF ALPHA=0.1;  
RUN;
```

Where ECG = QT/QTc population, SUBJID = subject number, TREAT = treatment (LOXO-305, moxifloxacin and placebo), TIME = nominal post-dose time point, BASE = baseline QTc, PERIOD = period, SEQUENCE = sequence, and DQTc = Δ QTc.

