6.8.1 Determination of Sample Size for Assay Sensitivity

To demonstrate assay sensitivity with concentration-QTc analysis, it has to be shown that the $\Delta\Delta QTc$ of a single dose of 400 mg moxifloxacin exceeds 5 ms (ie, the lower bound of the 2-sided 90% CI of the predicted QTc effect [$\Delta\Delta QTc$] should exceed 5 ms). In a similarly designed, recent crossover study with 24 healthy subjects (on-file data, ERT), the standard error (SE) for the prediction of the QT effect of moxifloxacin based on the concentration-QTc analysis was 1.24 ms. The within-subject SD of $\Delta QTcF$ in the referred study was 5.4 ms based on the by-timepoint analysis. If the effect of moxifloxacin is assumed to be 10 ms, the SE of 1.24 ms corresponds to an effect size of $(10-5)/(1.24 \times \sqrt{24}) = 0.82$, where the effect size is the effect assumed under the alternative hypothesis divided by the SD of the test variable. This value should be compared to the effect size of 0.62 required to guarantee a power of at least 90% in a paired t-test situation with a sample size of 24 evaluable subjects. In other words, based on this calculation, a power of at least 90% for 24 evaluable subjects will be obtained as long as the variability of the ΔQTc , as measured by its within-subject SD, does not exceed 7.1 ms (ie, 132% [= 0.82/0.62] of the 5.4 ms observed in the referred study assuming the ratio of effective sizes is

consistent with inverse ratio of within-subject SD). The number also agrees with recent recommendations of the FDA, which propose at least 20 subjects⁷.

7 References

3. Cleveland WS. Robust locally weighted regression and smoothing scatterplots. *J Am Stat Assoc*. 1979;74(368):829-836.

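### Optional low-cost improvement: if the primary concentration-QTc model fails to converge, SAP 6.2 drops the random slope without first trying it under a simpler covariance

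*SAP*

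**What the plan says.** SAP 6.2 specifies a random intercept and a random concentration slope per subject: "An unstructured covariance matrix will be specified for the random effects". The code is "RANDOM INT CONC /type=UN SUBJECT=SUBJID s", with no REPEATED statement and no PERIOD term. On degrees of freedom: "The degrees of freedom of estimates will be determined by the Kenward-Roger method". If the model fails to converge even after the concentrations are rescaled, "the random effect on the slope and intercept will be dropped, in this order, until convergence is achieved". Protocol 8.3.4 names the same random effects but gives no rule for non-convergence.

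The secondary model in SAP 6.4 is treated differently. It has a subject-within-period block, "REPEATED TIME / SUBJECT = PERIOD*SUBJID TYPE = UN", and on non-convergence "other covariance matrix such as compound symmetry and autoregressive will be considered".

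SAP 6.3 analyses moxifloxacin "using a similar model as for the primary analysis" and states no fallback order of its own.

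**The concern.** A subject's random intercept is common to the active and placebo periods, so it largely cancels from the active-minus-placebo contrast. Concentration is 0 on placebo, so the random slope is the only random term that separates the two periods. Two kinds of variation load onto it: a shift shared by all of a subject's readings in one period, and a true between-subject difference in slope. Once the slope is removed, the 13 active-period readings count as independent given the intercept, and the standard error of the predicted effect omits that variation.

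That standard error sets the upper bound compared with 10 ms. Misses fall on both sides, but the harmful one is clearing the drug when the true effect is near 10 ms. For moxifloxacin, a CI that is too narrow favours passing assay sensitivity.

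**Working it through.** **1. The plan's own figures.** SAP 6.8 assumes n = 24, a 3 ms effect, a 10 ms margin, SD 8 ms per treatment and one-sided 5%. With independent periods the SD of the difference is 8×√2 = 11.31 ms. The exact paired t-test power is 90.2%, and 24 is the smallest n that reaches 90%, so the stated power is reproduced. The sample size is not affected by this point.

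**2. Does such variance occur in this kind of data?** The documents give no variance components for LOXO-305. SAP 6.8.1 cites another 24-subject crossover study with a within-subject SD of 5.4 ms, where the standard error "for the prediction of the QT effect of moxifloxacin based on the concentration-QTc analysis was 1.24 ms".
- Paired contrast at one time point: 5.4×√2/√24 = 1.56 ms.
- The same averaged over 13 independent time points: 1.56/√13 = 0.43 ms.
- Simulated standard error of the planned model, independent residuals, moxifloxacin profile: 0.51 ms.
- Simulated with 40% of the within-subject variance shared within a period: 1.24 ms. With a slope SD of 5 ms at Cmax: 1.20 ms.

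Independent residuals therefore do not explain the cited 1.24 ms, provided that study used similar time points and a similar model.

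**3. What happens if the slope is dropped.** Data were simulated for 24 subjects with an active and a placebo period, and REML models were fitted.
- From the documents: 13 post-dose time points (SAP 4.1), within-subject SD 5.4 ms (SAP 6.8.1), and tmax 2 h with half-life 20 h (Protocol 1.4.2).
- Assumed: the variance split, intercept SD 5.9 ms, Cmax CV 35%, baseline SD 15 ms, and t with 23 df in place of Kenward-Roger.

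The nominal values are 90% coverage and 5% false clearance at a true 10 ms effect. Near-singular means a random-effect SD below 2% of the residual SD, or an absolute correlation above 0.995, in the unstructured fit.

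| Assumed source | Slope dropped: coverage / P(upper bound < 10 ms) | Near-singular fits |
|---|---|---|
| Neither | 90% / 4% | 64% |
| 2.5% shared | 86% / 6% | 35% |
| 5% shared | 81% / 8% | 17% |
| 10% shared | 73% / 12% | 3% |
| 25% shared | 58% / 19% | 0.1% |
| Slope SD 1 ms at Cmax | 87% / 6% | 39% |
| Slope SD 2 ms | 78% / 10% | 10% |
| Slope SD 3 ms | 66% / 16% | 1% |

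Each row has 1000 runs (Monte Carlo error at most 1.6 points). A diagonal intercept-plus-slope fit gave 88-93% / 3-6% in every row. A separate simulation with 400 runs per scenario gave 75% at 10% shared and 61% at slope SD 3 ms with the slope dropped, against 91-94% for the diagonal fit.

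**4. Hand check.** Coverage is roughly P(|Z| < 1.714 × model SE / actual SE), where 1.714 is the 95th percentile of t with 23 df.
- 10% shared, slope dropped: 1.714×0.45/0.71 = 1.09, about 72%. Diagonal: 1.714×0.69/0.72 = 1.64, about 90%.
- Slope SD 3 ms, slope dropped: 1.714×0.48/0.87 = 0.95, about 66%. Diagonal: 1.714×0.81/0.84 = 1.65, about 90%.

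**5. Effect over all trials.** The coverages in step 3 come from dropping the slope in every run. The table below counts a difference only in near-singular runs and compares dropping the slope with the diagonal fit.

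| Random effects | Near-singular fits | Extra false clearance at a true 10 ms |
|---|---|---|
| Uncorrelated | as in step 3 | 0-0.4 points (0-0.5 in the separate runs) |
| Slope SD 2 ms, correlation +0.5, intercept SD 5.9 ms | 22% | 0.9 points (about 0.8 in the separate runs) |
| Slope SD 2 ms, correlation +0.5, intercept SD 3 ms | 29% | 2.8 points |

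**6. Moxifloxacin.** At a true effect of exactly 5 ms, P(lower bound > 5 ms) with the slope dropped is 4% with neither source, 15% at 10% shared and 21% at 25% shared. The diagonal fit gives 3-6%.

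**The case against.** The strongest reply is that SAP 6.2 already has a complete, prespecified rule, and that the trigger and the harm mostly exclude each other. Near-singular fits are commonest (64%) where dropping the slope does no damage, and rare where the damage is large. At the 40% shared variance suggested by SAP 6.8.1 they occurred in 0 of 600 runs. At the planned 3 ms effect at least 99% of simulated trials pass under either model. SAP 6.4 also gives by-time-point intervals with a subject-within-period covariance, which could expose an implausibly narrow primary CI. All of this stands, and it is why the point is optional.

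Two further replies stand in part. The diagonal step is not a complete cure. When the slope variance is itself estimated at zero it gives the same answer as dropping the slope: in 29 near-singular runs at 10% shared, both gave 62% / 14%. And the wording of SAP 6.3 can be read as carrying the SAP 6.2 order over to moxifloxacin; the 15-21% figures also need a true effect of 5 ms, where SAP 6.8.1 assumes 10 ms.

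A reader might infer from the 58-75% coverages that the trial's primary CI is unreliable. The documents do not support that. Those figures hold only if the fallback is used, and the planned full model covered 88-94% in all scenarios. Nor does the 1.24 ms standard error show that this trial would be harmed: it concerns another drug in another study, and in that setting the fallback would seldom be reached.

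**Conclusion.** This is an optional improvement to a contingency rule, not a fault in the planned analysis. If the fallback is used while shared variance or slope variation is present, the primary 90% CI is too narrow: about 73-75% coverage at 10% shared variance and 61-66% at slope SD 3 ms, against about 88-94% with a diagonal covariance. With neither source present, the rule is sound.

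Across all trials the effect is small: about 0-0.5 points of extra false clearance at a true 10 ms effect with uncorrelated random effects. It reaches about 1-3 points only with a slope SD of 2 ms correlated +0.5 with the intercept, values that no passage supports.

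The variance components are assumed. The trigger is a near-singularity proxy, not actual PROC MIXED non-convergence, and the true rate of non-convergence is unknown. The case for the change is its low cost and the fact that it protects the interval used for the primary decision.

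**What to change.** In SAP 6.2, after rescaling and before any random effect is dropped, add a refit with `RANDOM INT CONC / TYPE=VC SUBJECT=SUBJID`. If the slope still has to be dropped, or its variance is estimated at zero, report a subject-clustered standard error (for example leave-one-subject-out) as a sensitivity analysis; in simulation this gave 88-93% coverage. A subject-by-period random intercept is a weaker substitute, at 84-87% when the slope SD is 2-3 ms. Report which step was used, and state in SAP 6.3 that the same order applies to moxifloxacin.

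The cost is a few sentences and one line of model code, plus a short program for the clustered standard error. If the planned model converges with a non-zero slope variance, nothing changes. The downside is a somewhat wider CI if the fallback is reached.
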